INL	Idaho National Laboratory
INQ	Interpersonal Needs Questionnaire
IRB	Institutional Review Board
ITHS	Institute of Translational Health Sciences
MHAPPS	Mental Health Among Patients, Providers, and Staff (short title of trial)
NIH	National Institutes of Health
NIMH	National Institute of Mental Health
OHRP	Office of Human Research Protections
PCORI	Patient Centered Outcomes Research Institute
PHI	Protected Health Information
PHQ-9	Patient Health Questionnaire-9
PHQ-A	Patient Health Questionnaire for Adolescents

MHAPPS Trial Protocol
SLHS Applied Research
December 30,2020

PI	Principal Investigator
PLES	People with Lived Experience with Suicide
SAE	Serious Adverse Event
SLHS	St. Luke's Health System
SPARC	Safety Planning Among Recipients of Care
UAP	Unanticipated Problem
US	United States
USPS Task Force	United States Preventive Services Task Force
VA	Veterans Administration
UW	University of Washington

Statement of Compliance

The trial will be conducted in accordance with International Council on Harmonisation Good Clinical Practice (ICH GCP), and the Patient Centered Outcomes Research Institute (PCORI) Terms and Conditions of Award. The Principal Investigators will assure that no deviation from, or changes to the protocol will take place without prior agreement from the funding agency and documented approval from the St. Luke's Institutional Review Board (IRB), except where necessary to eliminate an immediate hazard to the trial participants. All personnel involved in the conduct of this study have completed Human Subjects Protection and ICH GCP Training.

The protocol, informed consent form, recruitment materials, and all participant-facing materials will be submitted to the St. Luke's IRB for review and approval. Approval of the protocol and all relevant documents must be obtained before any participant is consented and enrolled in the study. In addition to St. Luke's Health System (SLHS) IRB approval, St. Luke's Research Final Authorization will be in place before study activities begin. Any amendment to the protocol or supporting documents will require review and approval by the IRB before the changes are implemented to the study. All changes to the consent forms will be IRB approved. Depending on the extent of changes, the research team and/or the IRB will determine whether participants who provided consent using a previously approved consent form need to be reconsented using the revised consent form.

Statement of Attribution for Protocol Template

1.1 Synopsis

Title	Mental Health Among Patients, Providers, and Staff (MHAPPS): Investigating the Mental Health Impact of COVID-19 and Comparing the Effectiveness of Two Caring Contact Interventions
Contract Number:	PCORI HIS-2018C3-14695
Study Description	Cross sectional survey (Aim 1) of mental distress in healthcare providers, staff, and patients in the COVID-19 era; and randomized controlled trial (Aim 2) comparing the effectiveness of two versions of a Caring Contacts intervention to reduce loneliness and mental distress.
Specific Aims	
Aim 1: Measure the prevalence of mental distress including loneliness, anxiety, depression, substance use, suicide ideation and other suicide-related risk factors in providers, employees, and patients served by SLHS. Describe differences associated with age, sex, race, ethnicity, urban or rural residence, living situation, occupation, local COVID-19 prevalence, perceived risk related to COVID-19, and masking and social distancing practices.
 
Aim 2: Compare the effectiveness of two versions of the Caring Contacts intervention ((1) introductory phone or video call followed by text messages (CC+), versus (2) text messages alone (CC)) to reduce loneliness and improve mental health outcomes among SLHS patients, providers, and staff experiencing mental distress during the COVID-19 era.

Outcomes	Aim 2 primary outcome: loneliness (NIH Toolbox Social Relationship Scales). ¹⁻³ Aim 2 secondary outcomes: suicide ideation (C-SSRS) ⁴⁻¹³ ; presence of risk factors for suicide including those theoretically related: defeat, entrapment, perceived burdensomeness, and thwarted belongingness (INQ) ^{14,15} ; background risk factors including stress (NIH Toolbox), ^{1-3,16} alcohol and illicit drug use, depression (PHQ-9), ¹⁷⁻¹⁹ and anxiety (GAD-7); ^{20,21} and attendance at mental healthcare appointments. All outcomes measured at 6 months following study enrollment.
Study Population	(1) SLHS providers and employees, and (2) adolescent and adult patients accessing primary care services from SLHS primary care clinics in Idaho. The study will enroll approximately 4,800 participants in the initial survey (Aim 1). The comparative effectiveness trial will be comprised of a subset of 660 participants who report elevated loneliness, suicide ideation, or other mental distress in the Aim 1 survey. Enrollment will be stratified by population (providers and employees; patients) with 165 per intervention arm in each stratum.

MHAPPS Trial Protocol

[figure not shown]
SLHS Applied Research

December 30,2020

Description of Study Sites	. (1) SLHS employs over 14,000 providers and staff across the system. (2) SLHS includes over 50 primary care clinics across the state of Idaho
Study Duration	This study will last for approximately 12 months, with 6 months for recruitment and 6 months for intervention/outcome assessment.
Participant Duration	Aim 1 is cross sectional (one timepoint). Aim 2 includes a 6-month long intervention period. Participants will complete a baseline assessment and an outcomes assessment at 6 months (end of intervention).

1.2 Schema / Study Flow Diagram

Figure 1: MHAPPS Trial Flow Diagram

MHAPPS Trial Protocol

SLHS Applied Research

December 30,2020

2. Research Question & Specific Aims

Research Question: How can health systems support mental health among providers, employees, and patients during the COVID-19 era while minimizing the burden on the health system?

Specific Aims.

- **Aim 1:** Measure the prevalence of mental distress including loneliness, anxiety, depression, substance use, suicide ideation and other suicide-related risk factors in providers, staff, and patients served by SLHS. Describe differences associated with age, sex, race, ethnicity, urban or rural residence, living situation, occupation, local COVID-19 prevalence, perceived risk related to COVID-19, and masking and social distancing practices.
- **Aim 2:** Compare the effectiveness of two versions of the Caring Contacts intervention ((1) introductory phone or video call (phone call) followed by text messages (CC+), versus (2) text messages alone (CC)) to reduce loneliness and improve mental health outcomes among SLHS patients, providers, and staff experiencing mental distress during the COVID-19 era.
 - **Aim 2 Hypothesis:** We hypothesize that including an introductory phone call with the Caring Contacts intervention will yield better mental health outcomes among providers, staff, and patients experiencing mental distress than a Caring Contacts intervention with no introductory phone call.

3. Introduction

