4.3 Masking

This trial will be single masked, with most members of the study team including the lead biostatistician masked to the comparator group (treatment condition) randomly assigned to each participant. Due to the nature of the intervention, masking interventionists or study participants to the comparator received is not feasible. The PI and research coordination team will conduct fidelity monitoring activities that may reveal the treatment assignment of individual participants.

5. Study Population

The study population for this research is adult and adolescent patients, and healthcare providers and staff from St. Luke's Health System in Idaho. Aim 1 will include up to approximately 2,400 patients and 2,400 providers and staff. Aim 2 will include a subset of 660 Aim 1 participants who report elevated levels of mental distress (330 patients, and 330 providers or staff). SLHS employs over 14,000 people

MHAPPS Trial Protocol

SLHS Applied Research

December 30,2020

and serves nearly half of the population of Idaho; a recent CDC report indicated that over 40% of adults reported elevated levels of mental distress during the COVID-19 pandemic. The source population is adequately large to meet this study's recruitment goals.

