5.4 Populations for Analyses

Analyses will be completed using the following populations:

1. **Intention to Treat (ITT) Analytic Population:** Data for all participants that complete study enrollment will be included in this dataset.
2. **Safety Analysis Population:** The dataset shared with the Data & Safety Monitoring Board for safety analysis will include data for all participants who completed study enrollment (e.g., the ITT Analytic Population Dataset).
3. **Per-Protocol Analysis Population:** Data for a subset of participants who were retained for the full study, were sent all 11 caring text messages, and received a phone call if randomized to the CC+ intervention (as outlined in protocol section 9) will be included in this dataset.
4. **Additional populations:** Additional datasets may be developed to complete sensitivity analyses, for example, where missing data have been imputed using different techniques.

6. Study Procedures

Aim 1: Cross Sectional Survey (Email REDCap survey link for providers and staff; send REDCap survey link via MyChart or email for patients)

- Aim 1 study enrollment and informed consent
- Aim 1 Survey
 - Demographics questions
 - C-SSRS (suicide risk)
 - NIH Toolbox Social Relationship Scales (loneliness, stress)
 - INQ (defeat, entrapment, perceived burdensomeness, and thwarted belongingness)
 - PHQ-9 (depression)
 - GAD-7 (anxiety)
 - COVID-19 beliefs and practices survey (brief)

Aim 2: Baseline / Enrollment (Subset of Aim 1 participants; see below)

- Aim 2 study enrollment and informed consent (phone call with Research Coordinator or study staff to complete via REDCap)
- Aim 2 Baseline assessments (Email or text REDCap survey link)
 - Baseline survey (Socio-economic status, gender identity, sexuality, religion, and alcohol and illicit drug use)
 - Expanded COVID-19 beliefs and practices survey (additional questions related to impact of COVID-19 on the individual, and his/her/their family, friends, and community)
 - Contact Sheet to collect alternative forms of contact for study participant

Aim 2: Caring Contacts Interventions (see description of interventions in section 9)

- **CC+:** 1 call, within 2 weeks of enrollment, and 11 caring text messages, sent from Hotline

follow-up specialists according to a standardized schedule over a 6-month period

- **CC:** 11 personalized caring text messages sent from Hotline follow-up specialists according to a standardized schedule over a 6-month period

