8.3.5 Alcohol and Illicit Drug Use

Alcohol and illicit-drug use will be measured at baseline and 6 months with questions adapted from the Youth Risk Behavior Survey.¹⁰⁷ Additional questions will be included to measure self-reported changes in alcohol or illicit-drug use since the beginning of the COVID-19 pandemic.

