12.1 Data Collection

All data for this study will be collected via online REDCap surveys. *Table 2* includes a list of all study variables, which aim they are associated with, and which tool will be used for assessment.

Table 2: MHAPPS Trial Variables & Other Data Elements

Variables			
Outcomes	Tool	Survey Collected	Source
Loneliness	NIH Toolbox – Social Relationship Scales - Loneliness Scale	Aim 1 Survey; Aim 2 Outcome Survey	REDCap
Suicidal ideation & behavior	C-SSRS Screener	Aim 1 Survey; Aim 2 Outcome Survey	REDCap
Recent suicide attempts, suicide completion, & self-harm; lethal means	6-Months Suicide Attempts Survey	Aim 1 Survey; Aim 2 Outcome Survey	REDCap
Perceived Burdenomeness; Thwarted Belongingness	INQ-15	Aim 1 Survey; Aim 2 Outcome Survey	REDCap
Stress	NIH Toolbox – Perceived Stress 10	Aim 1 Survey; Aim 2 Outcome Survey	REDCap
Alcohol and Illicit drug use	Youth Risk Behavior Survey Questions	Aim 2 Baseline Survey; Aim 2 Outcome survey	REDCap
Depression	PHQ-9	Aim 1 Survey; Aim 2 Outcome Survey	REDCap
Anxiety	GAD-7	Aim 1 Survey; Aim 2 Outcome Survey	REDCap
Uptake of outpatient mental health treatment	N/A	Aim 2 Baseline Survey; Aim 2 Outcome Survey	REDCap
Exposure Variables		Survey Collected	Source
Date of birth, age in years, age category (adult/peds)		Aim 1 Survey	REDCap

MHAPPS Trial Protocol

SLHS Applied Research

December 30,2020

Sex at birth	Aim 1 Survey	REDCap
Race and ethnicity	Aim 1 Survey	REDCap
Zip code of residence (urban/rural)	Aim 1 Survey	REDCap
Gender identity & sexuality	Aim 2 Baseline Survey	REDCap
Religion	Aim 2 Baseline Survey	REDCap
Variables related to employment and occupation of self/parent	Aim 1 Survey	REDCap
Education / maternal education	Aim 1 Survey	REDCap
Living situation (permanent, temporary)	Aim 1 Survey	REDCap
Number of people at home	Aim 1 Survey	REDCap
Caregiving for dependent(s)	Aim 1 Survey	REDCap
Financial security and food security	Aim 1 Survey; Aim 2 Baseline Survey	REDCap
Food access and eating habits and COVID-19	Aim 2 Baseline Survey	REDCap
Physical activity and COVID-19	Aim 2 Baseline Survey	REDCap
Perceived risk for COVID-19 & other COVID-19-related questions	Aim 1 Survey; Aim 2 Outcome Survey	REDCap
Masking practices & beliefs	Aim 1 Survey; Aim 2 Outcome Survey	REDCap
Social distancing practices & beliefs	Aim 1 Survey; Aim 2 Outcome Survey	REDCap
School attendance, extracurricular activities	Aim 2 Baseline Survey (Youth)	REDCap

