4 DATA SOURCE

All data for this study will be collected via online REDCap surveys. *Table 1* includes a list of all study variables, which aim they are associated with, and which tool will be used for assessment.

Table 1: MHAPPS Trial Variables & Other Data Elements

Variables			
Outcomes	Tool	Aim Collected	Source
Loneliness	NIH Toolbox – Social Relationship Scales - Loneliness Scale	Aim 1	REDCap
Suicidal ideation & behavior	C-SSRS Screener	Aim 1	REDCap
Recent suicide attempts, suicide completion, & self-harm; lethal means	6-Months Suicide Attempts Survey	Aim 1	REDCap
Perceived Burdensomeness; Thwarted Belongingness	INQ-15	Aim 1	REDCap
Stress	NIH Tool Box – Perceived Stress 10	Aim 1	REDCap
Alcohol and Illicit drug use	Youth Risk Behavior Survey Questions	Aim 2	REDCap
Depression	PHQ-9	Aim 1	REDCap
Anxiety	GAD-7	Aim 1	REDCap
Uptake of outpatient mental health treatment	n/a	Aim 2	REDCap
Exposure (Baseline)	Tool	Aim Collected	Source
Age in years, age category (adult/peds)	Baseline Survey	Aim 1	REDCap
Sex	Baseline Survey	Aim 1	REDCap
Race and ethnicity	Baseline Survey	Aim 1	REDCap

Address including Zip code of residence (urban/rural)	Baseline Survey	Aim 1	REDCap
County of residence (urban/rural)	Baseline Survey	Aim 1	REDCap
Gender identity & sexuality	Baseline Survey	Aim 2	REDCap
Religion	Baseline Survey	Aim 2	REDCap
Occupation	Baseline Survey	Aim 1	REDCap
Education	Baseline Survey	Aim 1	REDCap
Living Situation (permanent, temporary)	Baseline Survey	Aim 1	REDCap
Number of People at Home	Baseline Survey	Aim 1	REDCap
Perceived Risk for COVID-19	Baseline Survey	Aim 1	REDCap
Masking Practices	Baseline Survey	Aim 1	REDCap
Social Distancing Practices	Baseline Survey	Aim 1	REDCap
Domestic Violence	Baseline Survey	Aim 2	REDCap
Local COVID-19 Prevalence			CDC or Idaho Department of Health & Welfare Prevalence Data
Process Variables		Source	
Aim 1 proportion of eligible participants completing survey			REDCap
Aim 2 proportion of eligible participants enrolled			REDCap
Participant feedback on phone call (CC+ arm only)			REDCap
Participant feedback on content and timing of caring messages			REDCap
“Dose” of follow-up contact: timing, type (phone vs text), and			Mosio

number of attempted and successful contacts from the Hotline		
“Dose” of Caring Contact text messages: date/time of each text message sent (* 11 text messages)		Mosio
Other Variables	Tool	Source
Does cell phone on record belong exclusively to study participant or is it shared?	Baseline Survey	REDCap

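### Aim 1 promises the prevalence of substance use, but the alcohol and drug items are collected only in the Aim 2 surveys of trial enrollees, so this part of Aim 1 cannot be answered

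*Protocol*

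**What the plan says.** The protocol synopsis, protocol section 2 and SAP section 2 give essentially the same Aim 1: "Measure the prevalence of mental distress including loneliness, anxiety, depression, substance use, suicide ideation and other suicide-related risk factors in providers", staff (employees, in the synopsis) and patients. A second sentence promises to describe differences by age, sex, occupation, residence, COVID-19 practices and other factors.

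Protocol section 6 lists the Aim 1 survey as demographics, C-SSRS, NIH Toolbox loneliness and stress, INQ, PHQ-9, GAD-7 and, last, the "COVID-19 beliefs and practices survey (brief" version. Alcohol and drugs are not on that list. They appear in the next block, under the Aim 2 baseline assessments: "Baseline survey (Socio-economic status, gender identity, sexuality, religion, and alcohol and illicit drug use".

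Protocol Table 2 (section 12.1) gives the collection points for this variable as "Aim 2 Baseline Survey; Aim 2 Outcome survey". In SAP Table 1 the row "Alcohol and Illicit drug use", with the tool "Youth Risk Behavior Survey Questions", is marked Aim 2. Protocol section 8.3.5 says: "Alcohol and illicit-drug use will be measured at baseline and 6 months with questions adapted from the Youth Risk Behavior Survey".

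On who answers the Aim 2 surveys, protocol section 5 states: "Aim 2 will include a subset of 660 Aim 1 participants who report elevated levels of mental distress".

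**The concern.** An objective names a quantity, and the instrument that serves the objective does not measure it. Respondents who fall below every distress cut-off are never asked about alcohol or drugs. Their chance of being observed on this variable is zero, so weighting or modelling cannot recover a survey-population prevalence without outside data or an untestable assumption. The same gap defeats the promise to describe differences across groups for this condition.

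At the reporting stage two options would remain: leave a named Aim 1 quantity unreported, or substitute a figure from people selected for loneliness, stress, anxiety, depression or suicidality. Because the Aim 1 survey is given once, the omission is hard to repair after it has been fielded.

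**Working it through.** The documents give no target prevalence, precision or sample size for substance use in Aim 1, so there is no planned figure to reproduce. The check compares the aim with the data sources and then sizes the gap.

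**Step 1. Conditions named in Aim 1 against protocol Table 2**

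| Condition | In the Aim 1 survey? |
|---|---|
| Loneliness | Yes |
| Anxiety (GAD-7) | Yes |
| Depression (PHQ-9) | Yes |
| Suicide ideation (C-SSRS) | Yes |
| Other suicide-related risk factors (INQ-15, stress) | Yes |
| Substance use | No: Aim 2 baseline and Aim 2 outcome surveys |

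Substance use is the only named condition without an Aim 1 source. Section 8.3.5 speaks only of baseline, which alone could mean the Aim 1 survey. Section 6, Table 2 and SAP Table 1 all resolve it to Aim 2. The items are also asked at 6 months according to section 8.3.5 and Table 2, although the outcome-survey list in section 6 omits them. The same enrollees answer that survey, so coverage does not change.

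**Step 2. Coverage**

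Inputs: at most 660 enrollees (both documents); Aim 1 size about 4,800 (protocol synopsis) or up to 4,000 (SAP section 5).

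- 660 / 4,800 = 13.75%
- 660 / 4,000 = 16.5%

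All of these people met at least one Aim 2 distress criterion (protocol 5.1.2, SAP 5.2), did not opt out of contact (protocol 5.2) and enrolled. SAP 5.3 defines the Aim 1 analysis population as all survey completers.

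**Step 3. Bias if enrollee data stood in for the survey population**

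Let d be the distressed share of respondents, and p1 and p0 the prevalence of substance use in distressed and non-distressed respondents.

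- Target: d·p1 + (1-d)·p0
- Enrollee-only estimate, taking enrollees as representative of the distressed: p1
- Bias: p1 - [d·p1 + (1-d)·p0] = (1-d)(p1-p0)

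The documents give neither p1 nor p0, so the gaps below are assumptions. The value d = 0.40 is borrowed from the adult figure (over 40%) cited in protocol section 5. It is not the share that would meet this trial's five-way criterion.

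| Assumed gap p1-p0 (points) | Bias at d = 0.40 (points) |
|---|---|
| 0 | 0.60 × 0 = 0 |
| 5 | 0.60 × 5 = 3 |
| 10 | 0.60 × 10 = 6 |
| 20 | 0.60 × 20 = 12 |

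For a 10-point gap, the bias falls from 0.70 × 10 = 7 points at d = 0.30 to 0.50 × 10 = 5 points at d = 0.50. Further selection through willingness to enrol is ignored.

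**Step 4. Room in the Aim 1 survey**

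Item counts for the adult instruments, from protocol sections 8.2 and 8.3: loneliness 5, stress 10, INQ 15, PHQ-9 9, GAD-7 7, C-SSRS screener 6.

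5 + 10 + 15 + 9 + 7 + 6 = 52

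Demographics, COVID-19 questions and the three extra C-SSRS items come on top. Protocol section 15.1 limits the Aim 1 survey to 50 questions, and section 16.2.2 gives it 10 minutes.

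**The case against.** The best defence is that this is loose wording in an aim. Substance use is one term in an illustrative list, and no Aim 1 definition, precision target or model is attached to it. The operational text consistently treats it as a trial variable, which SAP 6.3 summarises as change from baseline to 6 months. The protocol calls Aim 2 the primary analysis (section 4.1.2), and nothing there is affected. This limits the weight of the point. It does not remove it: the term stands in the aim in three places, and every other condition in the list is measured in the survey.

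Three stronger readings are tempting, and the documents do not support them.

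- A reader might infer that the trial will publish a biased prevalence. No text proposes reporting enrollee data as Aim 1 prevalence, and SAP 5.3 ties the Aim 1 tabulations to survey completers. An unreported item is at least as likely, so the bias figures apply only if the substitution is made.
- A reader might infer that the association models in SAP 7.1 fail. SAP 7.1.2 covers primary and secondary outcomes, and SAP 6.3 makes alcohol and drug use exploratory, although protocol 8.3 calls it secondary. SAP 7.1.3 tests distress levels without naming substance use. On the SAP's own classification, no specified Aim 1 model includes it. What fails is the aim's general promise to describe differences.
- A reader might infer that the whole item set can simply move to Aim 1. SAP 6.3 describes several substances with status, amount, frequency and change, and the survey's stated length is already under strain. Moving the set would also replace a measurement taken at enrolment with an earlier one.

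**Conclusion.** The inconsistency is real and follows from the text alone: with the plan carried out exactly as written, the substance-use part of Aim 1 cannot be answered. Coverage is at most 13.75% of the protocol's Aim 1 sample, or 16.5% of the SAP's, with no one below the distress cut-offs. That conclusion needs no outside assumption. The 0 to 12 point range is conditional: it assumes d = 0.40, gaps of 0 to 20 points, enrollees who represent distressed respondents, and a decision to use their data as a stand-in. If substance use does not differ by distress, that bias is zero. The point is worth correcting because one of the two specific aims promises something that its survey does not collect. It leaves the other Aim 1 measures, the Aim 2 primary analysis and the trial's power untouched.

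**What to change.** Preferred: add a brief set of core alcohol and illicit-drug items, such as current/ever/never use, to the Aim 1 survey. Amend the survey list in protocol section 6, the row in protocol Table 2 and the aim-collected entry in SAP Table 1. Keep the fuller items in the Aim 2 baseline survey, so that the 6-month change is still measured from enrolment. This has to be done before the Aim 1 survey opens.

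The cost is a short amendment to both documents and a slightly longer survey. The 50-question and 10-minute limits must be checked first, because the listed adult instruments already total about 52 items.

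Fallback, if the items cannot be added: delete substance use from Aim 1 in the synopsis, protocol section 2 and SAP section 2, and report the Aim 2 data only as a description of distressed trial enrollees. This costs a text amendment and the loss of that prevalence estimate.
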